5.8 Criteria for diagnosis

Acute respiratory viral infection (ARVI) is an acute, local (in most cases) respiratory tract infection presenting with catarrhal inflammation of the upper respiratory tract and proceeding with fever, runny nose, sneezing, cough, sore throat, a violation of the general condition of different manifestations.

The patient or parents (legal representatives) may complain of acute rhinitis and / or cough and / or conjunctival hyperemia (catarrhal conjunctivitis) in combination with symptoms of rhinitis, pharyngitis. The disease usually begins acutely, often accompanied by an increase in body temperature to subfebrile values (37.5 °C — 38.0 °C). Febrile fever is more typical for influenza, adenovirus infection, and enterovirus infections. Elevated temperature in 82% of patients is reduced by the 2-3rd day of the disease; longer (up to 5-7 days) febrile is maintained during influenza and adenovirus infection [7]. An increase of fever intensity during the disease period, or appearance of severe intoxication symptoms may indicate the accession of a bacterial infection. Repeated raise of temperature after a short-term improvement often related to development of acute otitis media following the long-lasting runny nose.

Nasopharyngitis is characterized by complaints of nasal congestion, discharge from the nasal passages, nasopharynx discomfort: burning, tingling, dryness, often accumulation of mucous discharge, which in children, flowing down the posterior pharyngeal wall, can cause a productive cough. When inflammation spreads to the mucosa of auditory tubes (Eustachitis), clicking, noise and ear pain may occur, and a sense of hearing may decrease. Clinical course of nasopharyngitis has the following age features: in infants - fever, discharge from the nasal passages, sometimes - anxiety, difficulty in feeding and falling asleep. In older children, the typical manifestations are rhinitis symptoms (peak on day 3, duration up to 6-7 days), in 1 / 3-1 / 2 patients - sneezing and / or cough (peak on day 1, average duration - 6-8 days), rarely - headache (20% in the 1st and 15% - up to the 4th day) [8].

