7. STUDY DESIGN

7.1 Parameters evaluated during the study

This study assesses the efficacy and safety of nasal and sublingual spray Polyoxidonium[®] (active ingredient of Azoximer bromide) compared with placebo, as part of complex therapy for ARVI not requiring hospitalization in children aged 1–12 years.

Primary efficacy criterion:

- Fever duration period² $\delta = -0.52$ days will be considered as a superiority cut-off level. Axillary body temperature level ≤ 36.9 °C confirmed by two consecutive measurements (morning-evening/evening-morning) will be considered as the end of fever.

Secondary efficacy criteria:

- The dynamics of intoxication symptoms by Days 3, 8 of treatment, assessed according to the Symptom Assessment Scale.
- Assessment of the ongoing therapy efficacy by a physician at the end of treatment course (IMOS scale) - complete recovery (0 points), significant improvement (1 point), minor to moderate improvement (2 points), unchanged (3 points), worsening (4 points).
- Assessment of the ongoing therapy efficacy by the patient's parent/adoptive patient (IMOS scale) - excellent, good, satisfactory, not efficient - scores from 0 to 3.
- Number of cases of the antipyretic product (paracetamol) consumption for the entire study period.
- Number of patients' dropout patients due to the need to prescribe the antibacterial products.
- Number of patients (%) with body temperature normalization (presence of axillary body temperature ≤ 36.9 °C in two consecutive measurements (morning-evening/evening-morning) on Day 5 of therapy.
- Number of patients (%) with clinical pattern normalization on Day 5 of therapy according to the Symptom Assessment Scale (total ≤ 3 points)

Safety endpoints

Safety and tolerability assessments will be conducted throughout the entire study (from the moment of the first use of the study product/ placebo) on the following parameters:

² Axillary body temperature > 37.0 °C confirmed by two measurements (morning-evening/evening-morning)

- frequency of AEs occurrence recorded according to the data of spontaneous patients' reports, presence of complaints, and also to physical examination data, clinically significant deviations of laboratory and instrumental methods of examination from baseline values;

Conclusion on safety of the study product will be made after a statistical assessment of all AEs, including serious ones, which identified at least possible relation to the study product.

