8.2 Non-inclusion criteria

A patient will not be enrolled, if he/she meets at least one of the following criteria:

1. Suspicion on pneumonia, bacterial infection (including meningitis, sepsis, otitis media, sinusitis, urinary tract infection, etc.) or the presence of a disease requiring the prescription of antibacterial drugs, starting from the first day of the disease.
2. Suspicion on initial manifestations of diseases with symptoms similar to ARVI signs (other infectious diseases, flu-like syndrome at the debut of systemic connective tissue diseases and other pathology).
3. Positive express test for influenza or streptococcal infection.
4. Clinical symptoms of severe ARVI requiring hospitalization (fever ≥ 40 °C, signs of respiratory obstruction, severe hemodynamic/neurological disorders).
5. A history of or previously diagnosed primary and secondary immunodeficiency.
6. Cancer.
7. Acute infectious or non-infectious diseases (except for ARVI), as well as exacerbation or decompensation of chronic diseases (diabetes mellitus, infantile cerebral palsy, cystic fibrosis, primary ciliary dyskinesia, bronchopulmonary dysplasia, respiratory and ENT organ malformations, etc.) affecting the patient's ability to participate in a study.
8. .Sucrase/isomaltase deficiency, fructose intolerance, glucose-galactose malabsorption.
9. A history of allergy/hypersensitivity to any component of products used in treatment (including sensitivity to paracetamol, propacetamol hydrochloride (paracetamol prodrug)).
10. Use of drugs specified in Forbidden Therapy for 1 month prior to study entry.
11. Patients whose parents/adoptive parents, from the point of view of the study, will not fulfill the observation requirements during the study or observe the mode of study product administration.
12. Participation in other clinical studies of medicinal products for less than 3 months to the screening visit.
13. Pregnancy.
14. Any other medical or social condition that, in the opinion of the study physician, prevents the child from this study participation.

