9.1.3 Visit 2 (Day 3)

Visit 2 shall be held at the clinical center/at home. The Investigator needs to conduct the following study procedures:

- Collection of patient's complaints;
- Physical examination;
- Measurement of major vital signs (HR, RR, body temperature);
- Symptom Assessment Scale filling out
- Checking the diaries completion at home;
- Adverse events registration
- Assessment of concomitant therapy
- Assessment of compliance with prescribed therapy;
- Assessment of exclusion criteria.

Clinical signs of bacterial infection overlay should be evaluated by investigator at this visit. By the decision of investigator, the subject will be excluded from the study (if antibacterial therapy is required) or continue study participation and study treatment.

Upon the completion of all the procedures of Visit 2, the Investigator shall inform the patient about the next visit - Visit 3 (Day 8 ± 1), which will be held at the clinical center.

On Day 5 of therapy, in the patient's diary the Symptom Assessment Scale shall be filled in; this procedure will be performed by the parent/adoptive parent at home. To carry out this procedure on Visit 2, parents/adoptive parents shall be instructed on how to fill out this scale.

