9.3.1 Forbidden Therapy

The concomitant use of the following medicinal products and/or procedures will lead to the patient's exclusion:

- antiviral drugs;
- immunomodulators (except for the study product);
- antimicrobial agents;
- centrally acting antitussives (butamirate);
- local and systemic glucocorticoids;
- physiotherapeutic treatment.

In the case of taking drugs included in the section "Forbidden therapy", the patient's study participation will be terminated and treatment will continue according to the standard of care for this nosology (treatment will be similar to real clinical practice).

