9.4 Methods for monitoring compliance with procedures

Compliance of the study product / placebo (adherence to therapy) will be assessed at Visits 2 and 3 according to the patient's electronic diary by checking the data entered by the patient's parent about taking the drug.

On Visit 1, one bottle of the prescribed drug will be given to the patient's parent / adoptive parent.

At Visit 3, the vial of the prescribed drug must be returned by the patient's parent / adoptive parent to the study center.

Monitoring compliance with the protocol procedures during the study is carried out by the investigator

According to the draft Patient information leaflet for Polyoxidonium, during therapy, patients from 1 to 2 years should receive the drug by 1 injection x 2 times per day sublingual (14 drugs in total / 14 doses), patients from 2 to 5 years - intranasal 1 injection in each nasal passage x 2 times a day (14 applications total / 28 doses), patients from 5 to 8 years old - intranasal 1 injection in each nasal passage 3 times a day (21 applications total / 42 doses), patients from 8 to 12 years old - intranasal for 2 injections per each nasal passage 2 times a day (14 applications in total / 56 doses). Possible omissions of taking the drug during the study:

No more than two misses with 2-fold SP / placebo.

No more than four passes - with 3-fold use of SP / placebo.

These conditions will allow maintaining the level of compliance not lower than 80% [21 - 24].

If compliance is less than 80%, patient data will not be included in the efficacy analysis.

Dosage of antipyretic drugs will be assessed during the study according to the Patient's Diary - by checking the completed data by the patient's parent about taking the drug on visits 2 and 3.

On Visit 1, one vial of the prescribed antipyretic drug will be given to the patient's parent / adoptive parent.

On Visit 3, the vial of the prescribed antipyretic drug must be returned by the patient's parent / adoptive parent to the study site.

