The efficacy data analysis will be carried out in a population of patients who have undergone all the study procedures and completed it according to the Protocol (PP population). The safety population will consist of all patients who have received at least one dose of the study product, for which further safety surveillance data is provided (ITT population). The safety parameters evaluated during the study include the results of patient's general condition assessment, measurements of vital signs, a general physical examination, patient's examination, a clinical blood test, and urinalysis (compared to baseline values on Visit 0).

Throughout the study the following will be recorded:

- All study product related cases of AEs and SAEs (number, severity).
- All cases of early study termination due to the development of AEs/SAEs associated with the study product administration (number, severity).
- Local adverse reactions (number, severity, connection with the product). Safety parameters will be studied descriptively for each group.

The number of AEs and patients with AEs will be summarized by treatment groups, with a distribution by systems and selected terminology. Additional generalizations will be made on the severity, as well as the connection with the study product.

Early withdrawn patients will be presented in the Patients List and summarized by the main reason for withdrawn, and by each treatment group. Indicators of physiological functions and laboratory analyzes at the baseline (Visit 0), as well as their changes from the baseline (Visit 3), will be summarized by treatment groups. In addition, the tables of changes in laboratory analyzes based on the classification of values as low, normal or high, relative to the norm limits, will be summarized and presented by treatment groups.

Not available or missing data will not be replaced.

In addition to the standard summary analysis, the Sponsor may conduct the additional analyzes, if deemed necessary.

Interim analysis An interim analysis was not planned.

Groups for analysis

Safety population and Per-Protocol Population.

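### All efficacy analysis, including the primary superiority test, is confined to per-protocol completers, and no as-randomised efficacy analysis is prespecified

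*Combined protocol and SAP*

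**What the plan says.** The synopsis (statistical methods) and section 12.2 carry the same rule: "The efficacy data analysis will be carried out in a population of patients who have undergone all the study procedures and completed it" per protocol. Section 12.8 adds that per-protocol status requires full eligibility and strict adherence. Sections 12.2 and 12.8 define two analysis sets only, safety and per-protocol. The ITT label in 12.2 belongs to the safety set, and 12.4 uses that set for safety. Section 12.3, which holds the primary hypotheses and the confidence-interval rule, names no other population.

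Children can leave the efficacy set after randomisation in several ways:

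- Visit 2 (9.1.3): "the subject will be excluded from the study (if antibacterial therapy is required").
- Forbidden therapy (9.3.1): "The concomitant use of the following medicinal products and/or procedures will lead to" exclusion. The list includes antimicrobials.
- Compliance (9.4): "If compliance is less than 80%, patient data will not be included in the efficacy analysis".
- Significant deviations (13.3), including any skipped visit and an open category left to the investigator or sponsor.

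Missing data are not replaced (12.6). Section 7.1 also lists as a secondary efficacy criterion the number of "dropout patients due to the need to prescribe the antibacterial products". Section 12.2 tabulates early withdrawals descriptively by main reason and arm.

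**The concern.** Randomisation protects a comparison of the groups as they were randomised. Here the confirmatory claim rests entirely on a subset formed afterwards, and no as-randomised result is planned to check it against.

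The routes out of that subset are not plainly unrelated to outcome. Section 5.8 says: "An increase of fever intensity during the disease period, or appearance of severe intoxication symptoms may indicate the accession of a bacterial infection". Antibacterial need in turn leads to exclusion. That sentence concerns fever intensity and gives no figure for duration, so it shows only that removal can be related to the course of fever.

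The plan also conflicts with itself. A child who drops out for antibacterials is not a completer, so the antibacterial-dropout criterion is 0 versus 0 in the set assigned to efficacy. This defect needs no assumption about bias.

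**Working it through.** **Inputs from the documents.** Means 2.6 and 3.2 days, SD 0.2, margin -0.52, Z values 1.645 and 0.842 (12.1); 86 randomised per arm after a 10% dropout allowance (synopsis); success if the upper 95% limit for the difference is below -0.52 (12.3). The documents do not give the number of children removed in each arm or their fever durations. Those are assumed below.

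**1. The plan's own figure.** n = (1.645 + 0.842)² × 2 × 0.2² / (2.6 - 3.2 + 0.52)² = 6.185 × 0.08 / 0.0064 = 77.3, rounded up to 78. This reproduces. Then 78 × 1.1 = 85.8, giving 86, and 86 × 0.9 = 77.4. The trial is sized for completers.

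**2. Room above the margin.** 0.60 - 0.52 = 0.08 days.

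**3. Excess removals that equal that room.** If each removed child has D more fever days, an excess of x removals out of 86 in one arm shifts the difference by about xD/86. Setting this to 0.08 gives x = 0.08 × 86 / D:

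- D = 1: 6.9
- D = 2: 3.4
- D = 3: 2.3

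Added to means of 2.6 and 3.2, these D values give 3.6 to 6.2 days. Section 5.8 allows this range: "longer (up to 5-7 days) febrile is maintained during influenza and adenovirus infection". Influenza is largely screened out by 8.2 ("Positive express test for influenza or streptococcal infection"), so here the range concerns adenovirus.

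**4. Both directions at a true difference of -0.52.** Let each arm of 86 hold 4 + k children with 2 extra days. One arm removes all of them; the other removes 4 and keeps k among its 82 completers. The shift is 2k/82, which is 0.073 for k = 3 and 0.098 for k = 4. Success rates are simulated with a pooled-t interval for means; base SD is the SD before the long-fever children are added.

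| Excess removals in | Per-protocol difference (k = 3 / 4) | False success, SD 0.2 | SD 0.5 | SD 1.0 |
|---|---|---|---|---|
| Product arm | -0.59 / -0.62 | about 15-17% / 28-29% | 10% / 14% | 6% / 7-8% |
| Neither (balanced) | -0.52 | 2.5% | 2.5% | 2.5% |
| Placebo arm | -0.45 / -0.42 | below 1% | below 1% | below 1% |

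The same trials analysed as randomised, with full fever data, stay at -0.52 with false success at or below about 2.5%.

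**5. Lower bound.** With a lognormal fever time (mean 3.2, SD 0.2) and no long-fever tail, removing 10%, 20% or 30% of children still febrile after Day 3 from one arm shifts its mean by 0.005, 0.011 or 0.019 days. That is 6% to 24% of the 0.08.

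**6. Censoring at withdrawal.** In the product-arm scenario at SD 0.2, censoring removed children at Day 3 and taking a Kaplan-Meier restricted mean to 7 days gives -0.56 / -0.58 against a true -0.52. More than half of the bias remains, because the censoring is itself outcome-related.

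**The case against.** **Blinding.** Under 7.3.1 investigators and statisticians do not know the codes until database lock, and under 13.3 inclusion decisions precede database closure. This stands as a real mitigation: it makes deliberate selection by those parties unlikely. It is incomplete, because two sponsor roles hold the codes while sponsor representatives classify deviations, and because a treatment effect on antibacterial need can unbalance removals without any unblinding.

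**The large error rates are imposed.** This stands. A reader might infer that the plan has a false-success rate of 15-29%, or that completer analysis favours the product. The documents support neither. Those rates need unequal removal at equal fever and a tail 10 SDs long at the plan's SD (2 / 0.2). If a long-fever child is equally likely to be removed in either arm, false success is nominal (2.2-2.7%). In the mirror case the product is penalised: at a true -0.60, success is at most about 2.5%.

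**Antibacterial dropouts are not lost.** Also correct. The counts remain in the withdrawal table by reason and arm, but no test of them is planned in a set where they can differ from zero.

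**A later statistical document may add the analysis.** Section 12 foresees one, and it was not available for this review. Section 12.2 also permits extra sponsor analyses. Neither prespecifies an as-randomised comparison in the present text.

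**Conclusion.** The gap is established by the text: all efficacy inference, including the primary test, is in per-protocol completers, and no as-randomised efficacy analysis is prespecified. The antibacterial-dropout criterion is empty in its own analysis set. Both need correcting.

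The consequence for the primary result is not established. Its direction is unknown, and its size runs from nothing (balanced removal), through 0.005-0.019 days (no tail), to 0.07-0.10 days in either direction (3 or 4 excess removals at 2 assumed extra days). These are conditional illustrations, not an error rate of the plan. They show that a 0.08-day clearance leaves little room for imbalance in who is removed. Confidence is high for the textual gap only.

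**What to change.** 1. In 12.2 and 12.8, with matching edits in 9.4 and 13.3, make the primary efficacy set all randomised children who received at least one dose, analysed as randomised. Keep per-protocol as supportive.
2. Compare antibacterial dropouts over all randomised children with the chi-square or Fisher test already in 12.2.
3. Unless consent is withdrawn, continue the existing twice-daily temperature diary (9.2) to one fixed day after a child stops treatment or is excluded, and use those readings. Visit 3 has a window of ±1 day, so define that day by the calendar and not by the visit. Where readings are still missing, do not rely on censoring at withdrawal alone. Report sensitivity analyses in both directions: fever ends at last observation, and febrile to the fixed day. Keep the difference in mean days as the measure, since the -0.52 margin was set for means.
4. Restate power for this set.

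**Cost.** Items 1 and 2 are wording and programming. Item 3 adds diary entries for withdrawn children, and some will still be missing, since the early-withdrawal visit is best-effort (8.3). The larger cost is power, through dilution and a larger SD. If 7 of 86 children per arm had 2 extra days, the SD would be √(0.2² + 2² × 7/86 × 79/86) = 0.58. Success at a true -0.60 would then be about 15%, and 80% power would need (1.96 + 0.842)² × 2 × 0.58² / 0.08², about 825 per arm. This depends on the assumed tail, but it shows why the stated 80% should not be carried over unchecked.

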12.3 Efficacy data analysis

A superiority cut-off level $\delta = -0,52$ days was chosen to evaluate the principal efficacy parameter - fever duration. The choice is based on the results of earlier studies, which evaluated fever duration in similar cohorts of patients [4, 5].

Therein, the following statistical hypotheses will be verified:

- **Null-hypothesis (H_0):** efficacy of the study product does not exceed the efficacy of placebo:

$$H_0: \mu_o \geq \mu_p + \delta,$$

where, μ_o and μ_p - average fever and intoxication period in the main group (μ_o) and placebo group (μ_p);

- **Alternative hypothesis (H_A):** therapy with the study product is better than placebo therapy:

$$H_A: \mu_o < \mu_p + \delta$$

A comparison of parameters between two groups of patients can be performed by calculating the 95% confidence interval for the difference between μ_o and μ_p . Efficacy of the study product is considered higher compared with the efficacy of placebo, if the upper limit of 95% confidence interval for the difference between μ_o and μ_p values is less than - (minus) 0.52 days.

12.4 Safety data analysis

Safety population will be evaluated for all types of safety analysis.

Preferred terms of MEDDRA dictionary (Preferred Term) will be used for coding and presenting the Lists of adverse events and associated diseases. All adverse events in the aggregate, as well as serious adverse events, adverse events associated with the therapy, and on other significant adverse events (for example, on adverse events that led to the cancellation of study therapy) will be presented through descriptive statistics.

Comparison of treatment groups by the incidence of AEs will be carried by Fisher's exact test.

Clinical laboratory evaluations together with indication of changes from baseline will be presented through descriptive statistics for each visit.

Laboratory deviations beyond normal values will be marked. Lists and summary descriptions of clinically significant hematological laboratory abnormalities will be presented.

Vital signs together with indication of changes from baseline will also be presented through descriptive statistics for each visit.

For a statistical analysis of quantitative indicators, a preliminary assessment of compliance with the law of normal distribution according to the Shapiro-Wilk criterion will be made. When verifying statistical hypotheses, parametric criteria will be used for indicators with a normal distribution, and non-parametric criteria will be used for indicators which distribution differs from normal. Comparison of groups by quantitative indicators will be carried out by Student's t-test for independent samples in the case of a normal data distribution or the Mann-Whitney test in the case of a distribution other than normal. Comparison of indicators within the group between visits will be performed by T-test for related samples in the case of a normal data distribution, or the Wilcoxon test in the case of a distribution other than normal.

To describe the quantitative variables, the use of the following characteristics is planned: mean, standard deviation, median, quartile, minimum, maximum, coefficient of variation.

Qualitative variables will be analyzed by Pearson χ^2 test or Fisher's exact test (if the absolute frequency of the indicator is 5 or less in at least one of the subgroups). To describe categorical data, the use of percentages or shares is planned.

Differences at $p < 0.05$ will be considered statistically significant.

The selection of statistical analysis method will be determined by the type of source data, kind of distribution. The possibility of using a number of statistical methods will be assessed after the completion of data collection, since the nature of data distribution, sample homogeneity, etc. is unknown. In the course of the analysis, it is possible to expand the list of methods used, if it is necessary for high-quality data processing.

